Systemic inflammation is a risk factor for VTE,² and risk of VTE has been shown to be increased amongst individuals with chronic inflammatory conditions including inflammatory bowel disease (IBD) and rheumatoid arthritis (RA) compared to the general population.³⁻⁶ Evidence for differential VTE risk in other inflammatory diseases, notably psoriatic arthritis (PsA) and vasculitis, is more limited.⁴ Risk factors for VTE have been described in the general population, and include C-reactive protein (CRP), obesity, fractures, surgery and use of oral corticosteroids and hormone therapy,^{7, 8} but there has been little interrogation of patterns of VTE risk factors for individuals with chronic inflammatory conditions and their association with subsequent VTE.⁹

In this context we will set out to describe the prevalence of VTE risk factors in individuals with systemic inflammatory disorders in a contemporary real-world population, by disease type (IBD, RA, and PsA) and relative to a control population without systemic inflammatory disease. In the same cohorts we will further compare the influence of VTE risk factors on risk of VTE events in individuals with systemic inflammatory disorders.

Methods

Study design

We will perform a retrospective cohort study to compare VTE risk and VTE risk factors in adults with IBD, RA, and PsA and matched controls between January 1, 1998 and January 1, 2018, using a large UK primary care database.

Data source

The Royal College of General Practitioners Research (RCGP) and Surveillance Centre (RSC) database will be used for this study. The RCGP RSC cohort derives from a large network of GP

practices distributed across England and provides representative sample of the UK population.¹⁰

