The pre-specified outcomes include the time to incident VTE (either PE or DVT), time to PE, and time to DVT. These outcomes will be defined using Read codes that have been previously validated in a similar UK primary care database.¹⁹ Time to each outcome will be compared between individuals with a systemic inflammatory disorder and the matched control population, and across IBD, RA and PsA subgroups.

Baseline characteristics and VTE risk factors

Baseline measures will comprise sociodemographic characteristics, clinical features and biomarkers, selected based on clinical expertise and existing literature demonstrating an established association with VTE or evidence to support an association with VTE among individuals with systemic inflammatory disorders.^{4, 7} Socioeconomic status will be defined using the official national measure; the index of multiple deprivation (IMD).²⁰ This will be calculated at the point of data extraction, using patient postcode, with the resultant scores stratified by deprivation quintile. Ethnicity will be extracted from the primary care record and grouped into the major UK ethnic groups; white, black, Asian, mixed, and others.²¹ BMI will be defined as the most recently recorded measurement prior to the study start date. Smoking status and alcohol use will be defined using the most recently recorded data prior to the study start date. Diagnostic codes will be used to define the presence of comorbidities at baseline: hypertension, hyperlipidaemia, diabetes, peripheral vascular disease, cardiovascular disease (Atrial fibrillation, angina, myocardial infarction, congestive heart failure), cerebrovascular disease, cancer, chronic obstructive pulmonary disease, chronic kidney disease (stages 3–5), liver disease, recent hospitalisation, joint replacement, and fractures. Diabetes and diabetes type will be identified using an algorithm developed for use within the RCGP RSC database.²²

The Read codes used to describe cardiovascular disease within the RCGP RSC database have been previously reported.^{23, 24} We will also extract records of pregnancy and reduced mobility. Biomarkers and laboratory tests including cholesterol and blood pressure will be derived by taking the most recent value in the year before cohort entry.

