We will examine the following medications commonly used for the management of systemic inflammatory disorders: non-steroidal anti-inflammatory drugs (NSAIDs), oral corticosteroids, disease modifying anti-rheumatic drugs (DMARDs), other non-biologic immunosuppressant medications, and biologic therapies (where recorded). We will also include hormone therapy (hormonal contraceptives, hormone replacement therapy). We will also extract information on prescribing of antiplatelet agents (aspirin or adenosine diphosphate receptor inhibitors) and lipid lowering therapy (statins, fibrates, or ezetimibe). Prescribing at the study start date will be defined as the presence of an issued prescription in the three months preceding or one month after the date of diagnosis.

Statistical Analyses

We will describe the characteristics at baseline for individuals with IBD, RA and PsA separately in comparison to the matched unexposed cohort. We will evaluate differences in characteristics at entry between those with and without systemic inflammatory disease using the χ^2 test for categorical variables and the unpaired t-test for continuous data. All reported *P*-values will be two-sided.

Event rates for the primary and secondary outcomes will be compared in individuals with and without systemic inflammatory disease, calculated as the number of events divided by the total person-years of follow-up, and expressed as the number per 1000 person-years.

Risk of VTE

We will estimate the risk of VTE overall, and for PE and DVT separately, using unadjusted Cox proportional hazards models, stratified by matched set (exposed cohort versus unexposed cohort), to provide overall hazard ratios for the association with each outcome. Models will be subsequently adjusted for sociodemographic and clinical and VTE risk factors in

multivariable analysis. We will then repeat the same analyses for each autoimmune condition separately.

Predictors of VTE

Subsequently, we will run multivariable Cox models to examine the relative influence of individual VTE risk factors in the cohort with systemic inflammatory disease and control cohort. We will then explore the impact of changing platelet count over the study follow-up on VTE risk by including platelet count as a time varying exposure in survival models.

Sensitivity analysis

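### Surgery is named as a VTE risk factor, but joint replacement is the only operation with a covariate; other operations are captured at most indirectly through an undefined recent-hospitalisation item

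*Combined protocol and SAP*

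**What the plan says.** All references are to the combined protocol and SAP.

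- **Introduction.** The general-population risk factors for VTE are said to "include C-reactive protein (CRP), obesity, fractures, surgery and use of oral corticosteroids and hormone therapy". The aims that follow are to describe the prevalence of VTE risk factors by disease and against controls, and to compare their influence on VTE.
- **Baseline characteristics and VTE risk factors.** Measures are "selected based on clinical expertise and existing literature demonstrating an established association with VTE", or for evidence of an association in people with inflammatory disease. "Diagnostic codes will be used to define the presence of comorbidities at baseline", and the list that follows closes with "recent hospitalisation, joint replacement, and fractures". The section then adds: "We will also extract records of pregnancy and reduced mobility". The medication paragraph adds drugs only.
- **Statistical Analyses, Risk of VTE.** "Models will be subsequently adjusted for sociodemographic and clinical and VTE risk factors in" multivariable analysis. The covariates are given by category and are not listed model by model. The analyses are then repeated for each condition.
- **Statistical Analyses, Predictors of VTE.** In the inflammatory disease cohort and the control cohort, "we will run multivariable Cox models to examine the relative influence of individual VTE risk factors". Platelet count is the only time-varying covariate mentioned.

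**The concern.** By the plan's own selection rule surgery belongs among the baseline measures, and no reason is given for leaving it out. Two things are at stake.

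The first is certain. A study that sets out to describe VTE risk factors and compare their influence will have neither a prevalence nor an HR for one that its Introduction names. The gap is easiest to see in the IBD analysis, where an operation on the bowel has no variable.

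The second is conditional. If recent surgery is commoner among people with another predictor, that predictor's HR takes on part of the surgical risk. Oral corticosteroids are the obvious example: prescribing is measured from three months before to one month after diagnosis, so it can coincide with a recent operation.

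**Working it through.** **Step 1. Set the Introduction's risk factors beside the variables defined.**

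| Named in the Introduction | Variable in the plan |
|---|---|
| CRP | Not named; could fall under the open-ended biomarker wording |
| Obesity | BMI |
| Fractures | Listed comorbidity |
| Surgery | Joint replacement only |
| Oral corticosteroids | Listed medication |
| Hormone therapy | Listed medication |

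Surgery is the only non-laboratory factor in that sentence without a variable that matches it. The separate extraction of pregnancy and reduced mobility does not fill the gap, and neither does the medication list.

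**Step 2. Ask whether recent hospitalisation fills it.** It does in part. An inpatient operation shortly before baseline would normally count. However, the item has no window, does not separate surgical from medical admissions, and would miss day-case operations. It cannot yield an HR for surgery. The plan also lists joint replacement beside it, which suggests that it was not meant to stand for operations in general.

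**Step 3. Scale of possible confounding (illustration only).** The plan states no sample size, event count or effect size, so there is no figure to reproduce. Every input below is an assumption. For an omitted binary covariate, the HR of a correlated predictor is multiplied by

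[1 + p1(HR − 1)] / [1 + p0(HR − 1)],

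where p1 and p0 are the prevalences of recent non-joint surgery with and without the predictor, and HR is that of surgery for VTE. The second figure in each cell halves p1 and p0, as if adjustment for hospitalisation dealt with half of the operations.

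| HR for surgery | 2% v 1% | 5% v 1% | 10% v 2% |
|---|---|---|---|
| 2 | 1.01; 1.005 | 1.04; 1.02 | 1.08; 1.04 |
| 3 | 1.02; 1.01 | 1.08; 1.04 | 1.15; 1.08 |
| 5 | 1.04; 1.02 | 1.15; 1.08 | 1.30; 1.15 |

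Worked cells:
- HR 3, 5% v 1%: (1 + 0.05 × 2)/(1 + 0.01 × 2) = 1.10/1.02 = 1.08.
- HR 5, 10% v 2%: (1 + 0.10 × 4)/(1 + 0.02 × 4) = 1.40/1.08 = 1.30. With half captured: 1.20/1.04 = 1.15.

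An HR as high as 10 with 10% v 2% would give 1.90/1.18 = 1.61, or 1.45/1.09 = 1.33 with half captured.

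The formula also takes the surgical HR as constant. The flag is set at baseline and follow-up can last up to 20 years (1998 to 2018). If the effect of an operation fades, the average inflation over follow-up is smaller than shown.

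**The case against.** The strongest reply is that the Introduction's list is background and does not commit the study to modelling every item, that covariates are chosen partly on clinical expertise, and that recent hospitalisation already covers part of the ground. GP recording of operations is also likely to be incomplete, so the gain from a new flag is uncertain. Much of this stands as a limit on the consequences. It does not explain the omission, because the selection rule rests on established association with VTE and surgery is named as such a factor.

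Some stronger readings are tempting but not supported:

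- **Surgery is missing from every model.** A reader might infer this from the covariate list. The unadjusted models carry no covariates by design, the adjusted models are described only by category, and recent hospitalisation is a partial proxy.
- **Surgical risk is measured for rheumatoid and psoriatic arthritis but not for IBD.** One covariate list applies to all cohorts. Joint replacement is collected in IBD and in controls too, and other operations lack a variable in every cohort. Any imbalance is one of relevance, and the documents give no data on it.
- **Anaemia markers would absorb surgical risk.** Anaemia and haemoglobin are not planned covariates.
- **Procedures cannot be extracted because the list relies on diagnostic codes.** Joint replacement is itself a procedure on that list, so the wording shows no such limit.

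It is also fair to say that a baseline flag misses operations after cohort entry. That limits the remedy, but adjusting for later surgery has a problem of its own, since it may be a consequence of the disease.

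**Conclusion.** The point holds for what the plan can report. Followed as written, it gives neither the prevalence nor the HR of surgery, although surgery meets its stated rule for inclusion. This conclusion rests on the text alone.

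The effect on other HRs is possible but not established. For surgical HRs of 2 to 5 and the prevalences assumed above, the inflation runs from about 1.01 to 1.3, and to about 1.15 if hospitalisation captures half of the operations. It could be negligible or material. Upward bias also requires surgery to be commoner among people with the predictor in question, which the documents do not show. The change is worth making before extraction because it is cheap and serves a stated aim.

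**What to change.** Add a baseline covariate for recent major surgery to the section on baseline characteristics and VTE risk factors:

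- Define it from a list of Read procedure codes, with a separate flag for abdominal or bowel surgery. Keep joint replacement as its own item.
- State a look-back window that ends at cohort entry; for controls, that is the start of their matched counterpart's follow-up. No existing rule can be borrowed, since recent hospitalisation, joint replacement and fractures have no stated window. Exposed people can enter 180 days after registration, so a longer window would reach back before registration for some of them.
- State the window for recent hospitalisation at the same time, so that the overlap between the two items is clear.
- Name the covariate explicitly in the baseline tables, the adjusted models and the predictor models, for all cohorts.
- Do not adjust the main exposure HR for surgery after cohort entry. It may lie on the path from disease to VTE, and adjusting for it would change what is estimated.

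The cost is one more code list in an extraction already planned. The downside is incomplete GP recording of operations: some people who had surgery will be classed as not having had it, so the surgery HR may be diluted and some confounding will remain. State this as a limitation. If recording is judged too poor to use, the protocol should say that surgery was considered and left out for that reason.

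### Drug exposure is defined once, around diagnosis, with no rule to update it, so drug hazard ratios in the predictor models are likely diluted if read as effects of being on treatment

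*Combined protocol and SAP*

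**What the plan says.** All references are to the combined protocol and SAP.

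- **Drug definition** (Methods, Baseline characteristics and VTE risk factors): "Prescribing at the study start date will be defined as the presence of an issued prescription in the three months preceding or one month after" diagnosis. This is the only rule that turns prescriptions into exposure.
- **Drugs covered** (same section): "We will examine the following medications commonly used for the management of systemic inflammatory disorders", namely NSAIDs, oral corticosteroids, DMARDs, "other non-biologic immunosuppressant medications, and biologic therapies (where recorded"). Hormone therapy, antiplatelets and lipid-lowering drugs are added.
- **Drugs as risk factors** (Introduction): the established VTE risk factors listed include "surgery and use of oral corticosteroids and hormone therapy".
- **Predictor analysis** (Statistical Analyses, Predictors of VTE): "we will run multivariable Cox models to examine the relative influence of individual VTE risk factors", in the disease cohort and the control cohort. A further step studies changing platelet count "by including platelet count as a time varying exposure in survival models". No other covariate is described in that way.
- **Follow-up** (Study design; Definition of the matched unexposed cohort): the study runs "between January 1, 1998 and January 1, 2018". A patient leaves at study end, transfer, death or outcome. A change of drug does not end follow-up.
- **Sensitivity analysis**: the only one moves the start date to 2004. None concerns drug exposure.

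**The concern.** A four-month window sets a yes/no label that, as the plan reads, stays with the patient for the rest of follow-up. Someone who first receives a DMARD in the third month after diagnosis is a non-user throughout. Someone given one steroid course at diagnosis is a user throughout. Moving the window to cohort entry would not cure this, because the label would still be fixed.

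The Lay summary says the study should find which risk factors are most strongly linked to the excess risk and point to targets for reducing it. A comparison of that kind is distorted if exposures that come and go are measured with more error than stable ones. A real association with current steroid or hormone use could appear weak and be ranked below factors that were simply better measured.

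Biologics raise a separate difficulty. They enter only where the primary care record holds them, so having no record is not the same as having no use.

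**Working it through.** The documents give no drug HR, event count, power or duration of drug use, so there is no stated figure to reproduce. What follows is an illustration.

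**Inputs from the documents.** One exposure window per drug; maximum follow-up of 2018 − 1998 = 20 years; a general-population VTE rate of about 3 per 1000 patient-years (Introduction), used in the simulation.

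**Assumed inputs.** True current-use HR *H*; share of follow-up actually on the drug among baseline users (*s*) and among baseline non-users (*u*).

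**Step 1: dilution from starting and stopping.** With a constant background rate, and drug changes unrelated to prognosis, the HR for baseline status is approximately

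HR_obs = [1 + s(H − 1)] / [1 + u(H − 1)].

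For H = 2.0:

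| s | u | Calculation | HR_obs |
|---|---|---|---|
| 0.9 | 0.05 | 1.90/1.05 | 1.81 |
| 0.7 | 0.10 | 1.70/1.10 | 1.55 |
| 0.6 | 0.10 | 1.60/1.10 | 1.45 |
| 0.5 | 0.20 | 1.50/1.20 | 1.25 |
| 0.3 | 0.15 | 1.30/1.15 | 1.13 |
| 0.3 | 0.20 | 1.30/1.20 | 1.08 |

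The first row is persistent use with little later starting, and the loss there is modest. Over the pairs from 0.9/0.05 to 0.3/0.15, a true HR of 3.0 is seen as 2.80/1.10 = 2.55 down to 1.60/1.30 = 1.23. A protective HR of 0.7 is seen as 0.73/0.985 = 0.74 up to 0.91/0.955 = 0.95.

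**Step 2: simulation check.** One million patients, 20 years, 3 events per 1000 patient-years off drug, 30% users at baseline, 8% yearly loss, true HR 2.0. The figures are ratios of event rates.

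| Yearly start / stop rate | Baseline status | Time-updated status |
|---|---|---|
| 0 / 0 | 2.02 | 2.02 |
| 0.02 / 0.05 | 1.56 | 1.97 |
| 0.05 / 0.10 | 1.36 | 1.97 |
| 0.10 / 0.30 | 1.19 | 2.01 |
| 0.10 / 0 | 1.38 | 2.02 |

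With no drug changes the two agree. Later starting alone is enough to dilute the baseline figure.

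**Step 3: precision.** By Schoenfeld's formula, with two-sided alpha 0.05, 80% power and 20% users (all assumed), an HR of 2.0 needs 103 events. An observed HR of 1.55 needs 259, and 1.25 needs 986.

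**Step 4: switching.** Suppose drug A has a true HR of 1.2 and drug B 2.5. Baseline A users spend 40% of time on each; non-users spend 5% on each. The apparent HR for A is

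(0.4×1.2 + 0.4×2.5 + 0.2) / (0.05×1.2 + 0.05×2.5 + 0.9) = 1.680/1.085 = 1.55.

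That is further from 1 than the truth, so dilution is not guaranteed once switching is allowed.

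**The case against.** The strongest reply is that the plan never claims a current-treatment effect. The definition sits in a section on baseline characteristics, and BMI, smoking, comorbidities and biomarkers are also fixed at baseline. As a predictor, baseline status is legitimate. That stands, and it is why the baseline model should stay. But the plan does not say that this is the drug HRs' intended meaning, and the Lay summary's interest in causes and targets invites the other reading.

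A second reply is that time-updated drug use follows disease flares and hospital admission, which are themselves plausibly linked to VTE and have no planned updating. This also stands. Updating replaces some misclassification with time-dependent confounding of unknown size, so the two models should be shown together and the updated HRs called associations.

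Third, the absence of updating is inferred from silence, as is the entry of drugs into the predictor models. Both inferences are reasonable: the one definition is a fixed window, the one time-varying covariate is named, and steroids and hormone therapy are listed as VTE risk factors. A reader might go further and infer that the authors have ruled out updating. The text does not say that.

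A reader might also expect a null biologic HR to be reported as a finding. The plan does not specify a biologic HR and already flags incomplete recording.

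**Conclusion.** The point holds as a weakness of the predictor analysis. As written, the plan yields drug HRs for prescribing around diagnosis. Read as effects of being on treatment, they are likely to be too close to 1 because of later starting and stopping. For an assumed true HR of 2.0 the illustrative range is about 1.1 to 1.8. Every input to that range except the length of follow-up and the background rate is an assumption, and where the study would fall cannot be told from the documents.

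Two stronger readings are not supported. One is that all drug HRs must be biased towards 1: switching and flare-driven changes can act in either direction. The other is that the comparison of disease with matched controls is compromised: nothing here shows that the HRs in the Risk of VTE section are affected.

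**What to change.** **In the predictor models**, add time-updated current use of oral corticosteroids, hormone therapy, DMARDs and other non-biologic immunosuppressants. Build it from dated issued prescriptions, with a fixed and stated exposure window after each issue. Where duration is recorded, use end of supply plus a stated carry-over instead; the Data source section mentions prescriptions but not quantity or duration, so the fixed window is the safer default. Use the start-stop (counting-process) set-up that the time-varying platelet analysis needs.

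**Keep the baseline-status model alongside**, labelled as prediction from prescribing at baseline, and keep the baseline definition for the descriptive table.

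**Describe the time-updated HRs as associations**, and say that current use also tracks disease activity.

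**For biologics**, report recorded use as a lower bound and do not interpret any HR as a treatment association.

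The cost is extra programming on prescription data the database already holds, plus a second set of drug HRs whose confounding by disease activity must be explained.

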The RCGP RSC database contains information on clinical diagnoses, anthropometric measurements (e.g., body mass index; BMI), laboratory tests results, and prescriptions, coded with the Read coding system (a thesaurus of clinical terms).¹¹ UK general practice lends itself to this type of study because it is a registration-based system (each patient can only be registered with a single GP), it has been computerised since the 1990s, and pay-for-performance targets introduced in 2004 have resulted in consistent high-quality clinical data entry about chronic disease.¹² All RCGP RSC registered practices have electronic laboratory links; meaning all test results are automatically coded and uploaded to the GP computer system. Studies using RCGP RSC data have been published across a range of chronic diseases.¹³⁻¹⁵

Study population

Adult patients (aged ≥18) contributing to RCGP RCS primary care database between January 1, 1998 and January 1, 2018, will be eligible for inclusion.

Definition of the exposed cohort with systemic inflammatory disease

The exposed cohort will include all individuals with an existing or incident diagnosis of IBD, RA or PsA (systemic inflammatory diseases) in the RCGP RCS over the study period. IBD, RA or PsA will be identified using Read diagnostic codes previously validated in UK primary care studies.¹⁶⁻¹⁸ Follow-up for exposed individuals will begin on the latest of the date of diagnosis indicated by first diagnostic code, January 1 1998 or 180 days after practice registration.

Definition of the matched unexposed cohort

The matched unexposed cohort will be defined by matching individuals in the exposed cohort with individuals who were never diagnosed with a systemic inflammatory disease either prior to or during the study period by age and sex at GP practice level. Unexposed individuals will require at least one year of follow-up when matched to minimise the risk they had a nonrecorded existing diagnosis of a systemic inflammatory disease of interest. Follow-up for each matched individual will begin at the start of follow-up of their exposed counterpart.

Follow-up will end at the earliest of the study end-date (January 1, 2018), the date of patient transfer from an included practice, date of death, or the date an individual developed an outcome of interest.

Outcomes

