To check the sensitivity of findings to the date of introduction of the quality and outcomes framework (QOF), we will repeat the main analyses with the study follow-up for exposed individuals beginning on the latest of the date of diagnosis indicated by first diagnostic code, January 1 2004 or 180 days after practice registration.

All statistical analyses will be performed in R statistical package.

Ethics approval

Study approval will be requested from the Research Committee of the RCGP RSC. The study does not meet the requirements for formal ethics board review as defined using the NHS Health Research Authority research decision tool (http://www.hra-decisiontools.org.uk/research/).

Contributors

Research support for this project in several areas including data analysis, literature searching, and medication writing will be provided by Momentum Data. [name] and [name] of Momentum Data have contributed to the writing of this protocol and to the study design. Funding for these studies has been provided by Pfizer UK.

Scientific rigor and study registration

The team ethos at Momentum Data is to support the highest quality research, for patient benefit, with rigorous scientific standards. Publication bias remains an issue in observational studies. Therefore, if approval is granted the protocol will be registered as an observational study with ClinicalTrials.gov and made publicly available prior to the commencement of data analysis. Any protocol amendments will be published alongside this public record of the study and will be noted in any final publication with the rationale for the modification. Any changes will be assessed for the need for ethics approval and further RCGP RSC study approval; these will be sought if required.

References

3. Choi HK, Rho Y-H, Zhu Y, Cea-Soriano L, Aviña-Zubieta JA, Zhang Y. The risk of pulmonary embolism and deep vein thrombosis in rheumatoid arthritis: a UK population-based outpatient cohort study. *Annals of the Rheumatic Diseases* 2013; **72**(7): 1182-7.

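### Baseline prescribing is measured around the date of diagnosis, not the start of follow-up, which misplaces it for late entrants, includes follow-up time for others and leaves controls without a date

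*Combined protocol and SAP*

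**What the plan says.** All of this is in the Methods of the combined protocol and SAP.

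- **Drug definition** (Baseline characteristics and VTE risk factors, medications paragraph). The label names study start: "Prescribing at the study start date will be defined as the presence of an issued prescription". The window that follows is tied to another date: "an issued prescription in the three months preceding or one month after the date of diagnosis".
- **Exposed cohort.** It takes in "all individuals with an existing or incident diagnosis of IBD, RA or PsA". Follow-up is to "begin on the latest of the date of diagnosis indicated by first diagnostic code, January 1 1998 or 180 days after practice registration".
- **Matched unexposed cohort.** Controls are people "never diagnosed with a systemic inflammatory disease either prior to or during the study period". Their time origin is given: "Follow-up for each matched individual will begin at the start of follow-up of their exposed counterpart". No date is given for their prescribing window.
- **Other baseline measures.** BMI, smoking and alcohol are taken before the study start date, and biomarkers in the year before cohort entry. Drugs alone are tied to diagnosis.
- **Use of the variables.** Statistical Analyses compares "differences in characteristics at entry between those with and without systemic inflammatory disease". Predictors of VTE then models individual risk factors.
- **Sensitivity analysis.** Entry becomes the latest of the "date of diagnosis indicated by first diagnostic code, January 1 2004 or 180 days after practice registration". The drug window is not mentioned.

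**The concern.** A baseline covariate should describe the person at time zero, using only information available by then and by the same rule in both cohorts. This definition does none of the three for everyone, and the faults fall on different people.

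1. **Exposed people who enter well after diagnosis.** The window describes treatment around first diagnosis, possibly years before entry. Long-term continuous users may still be classified correctly; others may not.
2. **Exposed people who enter at or just after diagnosis, mainly incident cases.** Part of the window lies inside follow-up, so a prescription issued after an early VTE can count as baseline use.
3. **Controls.** They have no diagnosis date, so the rule gives them no value. Borrowing the counterpart's date is natural, but the text does not say whether that means diagnosis or entry, and two programmers could choose differently.

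The Introduction names oral corticosteroids and hormone therapy as VTE risk factors. Describing risk-factor prevalence against controls, and the influence of those factors on VTE, are stated aims. The drug rows of the baseline table and the predictor models are therefore directly exposed. The adjusted hazard ratios are exposed only if drugs are in the adjustment set, which the plan does not itemise.

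**Working it through.** The plan gives no figure to reproduce here, so the check is date arithmetic followed by an illustration.

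**Inputs from the plan.** Window: three months before to one month after diagnosis. Entry: the latest of diagnosis, 1 January 1998 or registration + 180 days. Background VTE rate: about 3 per 1000 patient-years (Introduction). I take three months as 91 days and one month as 30 days.

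**Step 1: where the window falls.** Let L be the lag in days from diagnosis to entry; L is never negative. Relative to entry, the window runs from −91 − L to 30 − L.

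- Days of follow-up inside the window = max(0, 30 − L).
- Days of the 91-day pre-entry quarter covered = 91 if L ≤ 30, otherwise max(0, 121 − L).

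| L (days) | Window relative to entry | Follow-up days included | Pre-entry quarter covered |
|---|---|---|---|
| 0 | −91 to +30 | 30 | 91/91 = 100% |
| 10 | −101 to +20 | 20 | 100% |
| 30 | −121 to 0 | 0 | 100% |
| 60 | −151 to −30 | 0 | 61/91 = 67% |
| 90 | −181 to −60 | 0 | 31/91 = 34% |
| 121 | −212 to −91 | 0 | 0 |
| 180 | −271 to −150 | 0 | 0 |

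Anyone diagnosed on or before registration has L of at least 180, so the window closes at least 150 days before entry. A person diagnosed on 1 January 1990 who enters on 1 January 1998 has L = 2922, and the window closes 2892 days (about 8 years) before entry.

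**Step 2: the 2004 sensitivity analysis.** Taken literally, the window stays at diagnosis while the earliest entry moves to 1 January 2004. Since 1 January 2004 minus 121 days is 2 September 2003, people diagnosed from 1 January 1998 to 2 September 2003 who entered at diagnosis in the main analysis now have no coverage of the quarter before entry. That span is 2191 − 121 = 2070 days, or 5.7 of the 20 study years (28%). This is a share of calendar time, not of patients.

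**Step 3: size of the look-ahead.** 0.003 × 30/365.25 gives 24.6 first-month events per 100,000 people, or about 49 if the rate is doubled.

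**Step 4: illustration of the misclassification.** Assumptions, none from the plan: true drug hazard ratio 2.0; use p = 0.15 both at diagnosis and at entry; incident cases classified correctly; all existing cases, a share s of the exposed, have L ≥ 121. With PPV the proportion of true users among those flagged and FOR the proportion among those not flagged, the observed hazard ratio is (1 + PPV)/(1 + FOR).

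- No data in the window for existing cases: PPV = 1, FOR = sp/[1 − (1 − s)p].
- Correlation r between status at diagnosis and at entry: PPV = (1 − s) + s[p + r(1 − p)], FOR = sp(1 − r).

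| Scenario | s = 0.3 | s = 0.5 | s = 0.7 |
|---|---|---|---|
| No data for existing cases | 1.90 | 1.85 | 1.80 |
| r = 0.5 | 1.83 | 1.72 | 1.62 |
| r = 0 (extreme) | 1.67 | 1.47 | 1.27 |

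For example, with r = 0.5 and s = 0.5: PPV = 0.5 + 0.5 × 0.575 = 0.7875, FOR = 0.5 × 0.15 × 0.5 = 0.0375, and 1.7875/1.0375 = 1.72.

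**The case against.** The strongest reply is that date of diagnosis is loose wording for the index date. The sentence opens by naming study start, the other baseline measures use study start or cohort entry, and the analysis section speaks of characteristics at entry. On that reading the window follows entry, controls share their counterpart's start, and the sensitivity analysis moves the window too. This may indeed be what was meant. But the cohort definition treats diagnosis and start of follow-up as separate dates, so the text does not support the shorthand. Accepting it would also place a month of follow-up inside baseline for every exposed person and control. Neither reading is sound.

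A second reply is that the post-diagnosis month may be deliberate. Treatment prompted by a new diagnosis is often issued after it, and closing the window at entry would record some incident cases as non-users. That cost is real, and the documents give no timing of treatment initiation from which to size it. It is better met by modelling such treatment as time-varying than by counting it as baseline.

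Third, the hazard ratios above concern drug effects within the exposed cohort, a follow-on analysis, and their inputs are assumed. Equal use at diagnosis and at entry is doubtful for drugs that treat the disease. This stands: the figures show direction and plausible scale, and are neither an estimate nor a bound. They do not quantify bias in the prevalence comparison or in the adjusted exposed-versus-unexposed hazard ratio.

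**Conclusion.** The concern holds. The rule is wrong as written: it contradicts its own label and cannot be applied to controls. Confidence in that is high, because it rests on the text and on date arithmetic alone.

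The effect on results cannot be sized, since the plan gives neither the share of existing cases nor drug use. The misplaced window for late entrants and the missing control date matter most; the look-ahead is minor in absolute terms. The unadjusted hazard ratios are unaffected. If drugs are covariates, the 2004 analysis read literally would change drug misclassification along with the start date, so a shift in its results could not be attributed to the introduction of QOF alone. This should be corrected before data are extracted, but it does not undermine the main design.

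**What to change.** Define baseline prescribing as at least one prescription issued in the three months up to and including each person's start of follow-up. For matched controls, use the exposed counterpart's start of follow-up. Remove the month after diagnosis from the definition. Use one index-date term for all baseline measures, and state that it moves with entry in the 2004 sensitivity analysis. If early post-diagnosis treatment is of interest, enter it as a time-varying exposure from the date of the prescription. State also whether drugs belong to the adjustment set.

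For exposed people the 180-day registration rule already keeps a three-month look-back inside registered time. The cost is a wording change and one changed anchor date in the extraction code. The trade-off is that drugs first issued just after an incident diagnosis no longer count as baseline use.
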